8.3 Exclusion criteria

Participants who meet any of the following exclusion criteria are not to be enrolled in this study.

- 1) Inability or unwillingness to provide informed consent or abide by the requirements of the study
- 2) Actively intoxicated.

Participants who meet any of the additional exclusion criteria are not to be treated in this study.

- 3) History of any of the following:
 - a) Clinical hepatic decompensation (i.e. ascites, encephalopathy or variceal haemorrhage)
 - b) Solid organ transplant
 - c) History of severe, life-threatening or other significant sensitivity to study drugs (glecaprevir/pibrentasvir/sofosbuvir) or any excipients of the study drugs
- 4) Creatinine clearance (CLcr) < 30 mL/min at screening (Cohort B only)
- 5) Pregnant or nursing female
- 6) Decompensated liver disease
- 7) Use of prohibited concomitant medications
- 8) Chronic use of systemically administered immunosuppressive agents (e.g. prednisone equivalent > 10 mg/day for >2 weeks)
- 9) Prior treatment failure with an NS5A based DAA regimen

9 Study design

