10.3 Prior and concomitant medications

The prescribing information for all concomitant drugs should be consulted and reviewed carefully. The determinations listed in the respective contraindicated, warning, and precaution sections must be respected in order to prevent any potentially serious and/or life-threatening drug interactions.

Drug-drug interactions for each participant should be assessed on <http://www.hep-druginteractions.org/>. In case of any questions on potential interactions with a drug, please contact the study principal investigator.

Use of medications listed below within 2 weeks or 10 half-lives, whichever is longer, prior to study drug administration is contra-indicated (see Tables 1 and 2):

Table 2 Contraindicated concomitant medications with glecaprevir/pibrentasvir

Drug Class	Drug(s) within Class that are Contraindicated	Clinical Comments
Anticoagulants	Dabigatran	May increase dabigatran concentration potentially increasing risk of bleeding
Anticonvulsants	Carbamazepine	May decrease DAA exposure leading to a potential loss of therapeutic activity.
Antimycobacterial	Rifampin	May decrease DAA exposure leading to a potential loss of therapeutic activity.
Ethinyl estradiol-containing products	Ethinyl estradiol-containing medications (such as combined oral contraceptives and hormone replacement therapy)	Potential for ALT elevation
Gastrointestinal pro-kinetic agent	Cisapride	
Herbal Product	St. John's Wort (Hypericum perforatum)	May decrease DAA exposure leading to a potential loss of therapeutic activity.
HIV non-nucleoside reverse transcriptase inhibitor	Efavirenz Etravirine Nevirapine	May decrease DAA exposure leading to a potential loss of therapeutic activity.
HIV protease inhibitor	Atazanavir Darunavir	Potential for ALT elevation
HMG-CoA Reductase Inhibitors *	Atorvastatin Lovastatin Simvastatin	Potential for myopathy including rhabdomyolysis.

Immunosuppressant	Cyclosporin	Co-administration not recommended with cyclosporin dose >100mg per day
-------------------	-------------	--

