15.1 Primary endpoint

Proportion of patients achieving confirmed SVR12 (defined as HCV RNA below the lower limit of quantitation at 12 weeks post treatment) in the intention-to-treat population (defined as all enrolled participants who received at least one dose of study drug). The ITT population consisting of patients commencing inpatient DAA treatment within public hospital services

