15.2 Secondary Endpoints

- Proportion of patients with HCV RNA below the level of detection at 12 weeks post-treatment (SVR12) within each cohort by both ITT and PP analyses
- Proportion of patients with HCV below LLOQ at week 4 of therapy and ETR
- Proportion of patients completing DAA treatment course
- Proportion of patients with full (100%) and partial adherence (<50%, 50-80%, 81-99%) during treatment as assessed by in hospital medication charts and outpatient weekly self-report
- Uptake of DAA therapy during admission in patients suitable for study
- Safety: Rates and predictors of adverse events secondary to drug:drug interactions
- Sensitivity and specificity of finger prick POC testing compared to plasma HCV RNA at screening
- Proportion of patients completing recommended inpatient stay
- Changes in HRQOL
- Rates of re-attendance at subsequent planned study visits
- Rates and predictors of reinfection during follow-up

In those with a history of injecting drug use:

- Proportion of patients undergoing D&A evaluation during admission
- Proportion of patients initiating OST during admission
- Frequency and patterns of injecting behaviour following therapy for HCV

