15.3 Analyses

Proportions and 95% confidence intervals will be reported for both the primary and secondary virological endpoints. These will be assessed for both the PP and the ITT populations. Results will be stratified by HCV genotype/subtype.

Sub-group analysis of treatment efficacy (SVR12) in the ITT population will be evaluated for the following variables: demographic factors (age, gender); virological factors (pre-treatment HCV RNA, genotype); HIV co-infection. Additional treatment efficacy evaluations will be conducted among the per protocol study population, defined as Participants who receive >80% of planned treatment.

The impact of adherence (<50%, 50-80%, 81-99%), 100/100 adherence, on-treatment adherence and early discontinuation on SVR will also be evaluated.

A final full statistical analysis plan will be written and signed off by the Protocol Steering Committee prior to final study data lock.

16 Data Safety and Monitoring Board (DSMB)

This project is conducted as a Phase IV trial using PBS approved medication and as such, a DSMB will not be used. The medical monitor, [name] will oversee all serious adverse events for TOPIC. As [name] is also Co-Investigator and clinician at Prince of Wales Hospital, which is one of the recruiting sites, should an SAE occur in a patient under [name] care, the

project team will seek an independent review of the SAE from a suitably qualified independent Infectious Diseases Specialist or Hepatologist.

17 Data collection, source documents and record retention

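### The per-protocol set is defined by the amount of treatment received alone, so ineligible participants and those on drugs listed as possibly lowering exposure to their regimen stay in the per-protocol SVR12

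*Protocol*

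**What the plan says.** Section 15.1 defines the intention-to-treat population as "defined as all enrolled participants who received at least one dose of study drug"; the primary endpoint is SVR12 in that population.

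The per-protocol population is defined once, in section 15.3: "among the per protocol study population, defined as Participants who receive >80% of planned treatment". It has three uses. Section 15.3 says of the virological proportions and confidence intervals that "These will be assessed for both the PP and the ITT populations". Section 15.2 lists SVR12 "within each cohort by both ITT and PP analyses" as a secondary endpoint. The opening of section 15 has the cohorts evaluated one after the other and then together, by both approaches.

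Other sections say who should not be treated and which drugs may weaken treatment:

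- Section 8.2 requires, among other things, documented non-cirrhotic status.
- Section 8.3 introduces exclusions 3 to 9 with "Participants who meet any of the additional exclusion criteria are not to be treated in this study". They include use of prohibited concomitant medication (7) and earlier failure of an NS5A-based regimen (9).
- Section 10.3, Tables 2 and 3, gives for several drugs the comment "May decrease DAA exposure leading to a potential loss of therapeutic activity". Modafinil, in Table 3, has its own wording to similar effect.

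The definition in section 15.3 refers to none of these.

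**The concern.** A per-protocol estimate is normally read as the response among people who were eligible and were treated as planned. The set in section 15.3 selects on adherence only. Someone with an earlier NS5A failure, someone with cirrhosis treated in error, or someone taking an enzyme inducer listed in section 10.3 is labelled per protocol if the tablets were taken. If the virus returns in such a person, the failure is attributed to the regimen.

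No other stated analysis separates these cases. The one interaction endpoint concerns harm: "Safety: Rates and predictors of adverse events secondary to drug:drug interactions". The subgroups in section 15.3 are age, gender, pre-treatment HCV RNA, genotype and HIV co-infection, with no term for co-medication or eligibility. The adherence analysis again measures only the quantity of drug.

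This matters most for Cohort B, because whether four weeks of treatment suffice is the open question and Table 3 adds drugs that are not in Table 2.

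**Working it through.** **What the rule admits.** Assuming one dose a day, more than 80% of planned treatment means:

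- Cohort A: 0.80 × 56 = 44.8, so at least 45 of 56 daily doses.
- Cohort B: 0.80 × 28 = 22.4, so at least 23 of 28 daily doses.

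Nothing else is checked.

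**Inputs from the protocol.** 30 participants per cohort (section 15); the definition (section 15.3); an SVR above 95% cited for eight weeks of G/P in patients without cirrhosis (section 5). The protocol states no formal sample size, so there is no figure of its own to reproduce.

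**Assumptions, not in the protocol.** Per-protocol size n = 24 or 30 per cohort; one failure among participants without a breach; k = 1 to 3 participants in breach who received more than 80% of treatment and failed. k = 0 is equally compatible with the text.

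**Formula.** The number of successes is s = n − k − 1. With the breaches kept, the estimate is s/n; with them removed, s/(n − k). The difference is s·k / [n(n − k)]. For n = 30 and k = 1 this is 28 × 1 / (30 × 29) = 3.2 points. Intervals are exact (Clopper-Pearson) 95%.

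| n | k | Kept | Removed | Difference (points) |
|---|---|---|---|---|
| 30 | 1 | 28/30 = 93.3% (77.9–99.2) | 28/29 = 96.6% (82.2–99.9) | 3.2 |
| 30 | 2 | 27/30 = 90.0% (73.5–97.9) | 27/28 = 96.4% (81.7–99.9) | 6.4 |
| 30 | 3 | 26/30 = 86.7% (69.3–96.2) | 26/27 = 96.3% (81.0–99.9) | 9.6 |
| 24 | 1 | 22/24 = 91.7% (73.0–99.0) | 22/23 = 95.7% (78.1–99.9) | 4.0 |
| 24 | 2 | 21/24 = 87.5% (67.6–97.3) | 21/22 = 95.5% (77.2–99.9) | 8.0 |
| 24 | 3 | 20/24 = 83.3% (62.6–95.3) | 20/21 = 95.2% (76.2–99.9) | 11.9 |

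Each failure kept therefore costs about 3.2 points at n = 30 and 4.0 at n = 24. At n = 30, one failure moves the point estimate from just above the cited 95% to just below it.

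**If those in breach respond.** Start from 28/30 = 93.3% and remove one, two or three responders: 27/29 = 93.1%, 26/28 = 92.9%, 25/27 = 92.6%. Keeping them raises the estimate by 0.2 to 0.7 points.

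**The case against.** **This belongs in the analysis plan.** Section 15.3 promises a full statistical analysis plan before data lock, and sorting major deviations is commonly done there. That would answer a complaint that the protocol is silent, but the protocol is not silent: it states a definition. A later plan may narrow it, but would then depart from the protocol's own wording.

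**A set based on treatment received is a legitimate choice.** It is, and it is worth reporting. It answers a question about adherence, however, whereas section 15.3 uses it for efficacy and calls it per protocol.

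**There may be no such participants.** This stands. Section 8.3 bars their treatment, section 10.3 requires an interaction check for each participant, and section 11 repeats the check at baseline and on treatment. The protocol gives no breach rate.

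**The consequence is limited.** This also stands. The primary endpoint is intention-to-treat, no test or decision rule rests on the per-protocol figure, and the intervals in each comparison overlap widely. Genotyping and sequencing of recurrent viraemia help tell relapse from reinfection, but no planned analysis links a relapse to co-medication.

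**A stronger reading.** A reader might infer that the per-protocol SVR12 will be biased downward. The documents do not support that. Tables 2 and 3 speak only of a possible decrease and a potential loss of activity. Several exclusions, such as pregnancy, have no stated link to efficacy. Participants in breach who respond push the figure up. A lower estimate is the likelier direction if interactions do occur, but it is not established.

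**Conclusion.** The definition in section 15.3 is fixed too loosely for the use made of it. It keeps participants treated in breach of eligibility, or exposed to a drug listed as possibly weakening their own regimen, in a named secondary efficacy estimate. Any failure among them would lower that cohort's per-protocol SVR12 by about 3 to 4 points each, given 24 to 30 participants in the set and one other failure. The number of such failures is assumed and may be zero; responders in breach shift the result by well under one point in the other direction. The primary result does not change. This is a low-cost improvement to a secondary analysis, not a flaw that threatens the trial's main conclusion.

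**What to change.** Redefine the per-protocol set in section 15.3 as participants who:

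- (a) received >80% of planned treatment;
- (b) met the eligibility criteria for treatment at first dose, that is, the inclusion criteria as qualified by the footnote to section 8.2, including non-cirrhotic status, and none of exclusions 3 to 9 as they apply to the cohort;
- (c) had no recorded use, between first and last dose, of a drug listed as decreasing exposure to a component of their own regimen: Table 2 for Cohort A, Tables 2 and 3 for Cohort B.

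Condition (c) must be specific to the cohort because Cohort A receives no sofosbuvir. Phenytoin and rifabutin, for example, appear only in Table 3. Entries listed for other reasons, such as ALT elevation or myopathy, do not fall under (c).

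Classify deviations before SVR12 results are reviewed, since the study is open-label. Report the >80%-only set as a sensitivity analysis.

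Section 10.3 words the restriction as use before study drug is given, whereas section 11 assesses interactions on treatment as well. These passages must be reconciled so that it is clear what counts as a deviation. No clinical rule is proposed here.

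The cost is one revised definition and a deviation review. No new data are needed: eligibility is established before dosing, and concomitant medication is already scheduled at screening, baseline, discharge, on-treatment visits and SVR12. The set may lose a few participants per cohort, with slightly wider intervals.

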17.1 Submission of data

Following each participant visit the designated site staff will complete the visit specific eCRF. Once all required information is received the eCRF shall be considered complete. Project Team staff will then monitor the data for completeness and accuracy. Any eCRF discrepancies, either manual or automatic, will be addressed with the site staff for clarification.

The site Principal Investigator is responsible for ensuring the completion of accurate source documentation to support data collected on case report forms. Source documents include all recordings of observations or notations of clinical activities and all reports and records necessary for the evaluation and reconstruction of the trial. Source documents include, but are not limited to; participant medical records, laboratory reports, ECG tracings, X-rays, radiologist reports, participant diaries, biopsy reports, ultrasound images, participant progress notes, pharmacy records and any other reports or records of procedures performed in accordance with the protocol.

It is not acceptable for the CRF to be the only record of study participation and progress must also be recorded in the each person's medical record. This is to ensure that anyone accessing the medical record has adequate knowledge that the person is a clinical trial participant.

Any document that acts as a source document (the point of the initial recording of a piece of data) should be signed and dated by the person recording or reviewing the data for issues of medical significance (for example the review of laboratory reports). Persons signing the source documents must be listed as a site staff member.

The sponsor's monitor may visit sites to conduct source document verification. The number of visits will depend upon the recruitment rate.

The site Principal Investigator is responsible for retaining all the essential documents listed in ICH Good Clinical Practice guidelines. These must be organised in a comprehensive filing system that is accessible to study monitors and other relevant personnel.

18 Archiving

The site Principal Investigator is responsible for ensuring all study documents are retained for a minimum of 15 years following completion and publication of the study.

19 Ethics committee/regulatory approval and informed consent

The sponsor is responsible for ensuring regulatory approval for the study is obtained.

The site Principal Investigator is responsible for obtaining IRB/EC approval for the protocol and participant information and informed consent form in compliance with local regulatory requirements prior to entering any participant into the study. The approval letter/document must clearly identify the protocol and all documents approved by the IRB/EC including version number & date of the protocol and participant information and consent form. A copy of the approval document must be sent to the study sponsor.

The site Principal Investigator must also obtain approval for any amendments to the protocol or participant information and informed consent form. The Principal Investigator must comply with all IRB/EC reporting requirements for all adverse events, annual updates and end of study reports and must agree to abide by any IRB/EC conditions of approval.

The site Principal Investigator (or designee) is responsible for ensuring freely-given consent is obtained from each potential participant prior to the conduct of any protocol-specific procedures. The Principal Investigator may delegate the task of obtaining consent to appropriately qualified Sub-investigator(s). Consent must be documented by the participant's dated signature on the

participant information and consent form together with the dated signature of the person conducting the consent discussion.

If the participant is illiterate, an impartial witness should be present during the entire consent discussion. Once the discussion is complete, the participant must sign and date the informed consent form, if capable. The impartial witness must also sign and date the consent form along with the person who conducted the consent discussion.

If the participant is legally incompetent (i.e. under 18 years of age or mentally incapacitated) the written consent of a parent, guardian or legally authorised representative must be obtained.

A copy of the signed and dated participant information and consent form must be given to the person prior to study participation. The participant or their legally authorised representative must be informed in a timely manner of any new information that becomes available during the course of the study that may affect his/her willingness to continue study participation.

This study shall be conducted in accordance with the ethical principles laid out in the Declaration of Helsinki (most current issued version) and the National Statement on Ethical Conduct in Research Involving Humans (most current issued version).

20 Confidentiality of data

Confidentiality of participant records

Participant confidentiality will be maintained at all times and no documents containing the participant's name or other identifying information will be collected by the sponsor. It may be necessary for the sponsor's representatives, the IRB/EC and regulatory authority representatives to have direct access to the participant's medical records. If study documents need to be photocopied during the process of verifying case report form data, the participant will be identified by a unique code only; full names and other identifying information will be masked.

Confidentiality of study data

By signing the Clinical Trial Agreement, the site Principal Investigator affirms to the sponsor that information provided to them by the sponsor will be maintained in confidence and divulged only as necessary to the ethics committee and institution employees directly involved in the study. Both ethics committee members and employees must also understand the confidentiality requirements for any information divulged to them. The data generated by this study will be considered confidential, except where it is included in a publication as agreed in the publication policy of this protocol.

At sites where regulations restrict the collection of full date of birth and/or participant initials, the following conventions will be used:

- Date of birth will be entered as 01/01/YYYY
- Initials will be entered as AA-AA, BB-BB, CC-CC etc.

21 Governance

This national research protocol is funded by Kirby Institute UNSW Sydney. The study drugs will be accessed via the PBS. The study is sponsored by the University of New South Wales (UNSW) and coordinated through the Kirby Institute for infection and immunity in society. The Kirby Institute has established governance and implementation structures which use resources efficiently to deliver program objectives on schedule.

22 Quality Control (QC) and Quality Assurance (QA)

